9.3.1 Evaluable for Toxicity

All participants will be evaluable for toxicity from the time of their first study vaccination.

9.3.2 Evaluable Non-Target Disease Response

Not applicable

9.4 STATISTICAL ANALYSES

9.4.1 General Approach

Most analyses will result in estimates of binary endpoints and will be presented as proportions and corresponding exact 95% confidence intervals.

Exploratory endpoints, such as mechanistic endpoints, will be presented as means with standard deviations and/or as medians and interquartile ranges. Graphical presentation may be useful.

While hypothesis testing is likely to be limited in scope, two-sided p-values with alpha=.05 will be used, with appropriate cautions regarding interpretation due to multiplicity.

9.4.2 Analysis of the Primary Endpoints

The primary endpoint will be estimated using the proportion of reaction to the active vaccine, and presented with a 95% confidence interval, using the Clopper-Pearson method.

It is not anticipated that individuals randomized to receive placebo vaccination first will not get the active vaccine, but if this occurs, the following approaches will be used: i) analysis in the population with complete data (which will be the primary approach), and ii) analysis where missing data is imputed to be a vaccine reaction.

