Prior to enrollment, participants will be screened remotely by phone/email and/or videoconference (using an NIH-approved platform) to assess eligibility and to ensure co-morbid allergic and other diseases, including asthma and atopic dermatitis, are well-controlled and disease activity is stable. If individuals have co-morbid conditions that may increase their risk of having a severe allergic reaction, they may be asked to come to the NIH CC for additional studies, such as pulmonary function testing, echocardiogram, or blood laboratory testing, that are felt to be clinically necessary (based on the discretion of the study team) to ensure that they are medically stable to undergo the study intervention. After screening, eligible individuals will be enrolled and admitted to the NIH CC ICU on day 0. Two IV lines will be inserted prior to study vaccination to allow for frequent blood draws and rapid administration of fluids/medications if needed in the event of a reaction. We will aim to admit subjects so that their first study vaccination occurs as close as possible to when the second dose of vaccine is indicated (i.e., 21 days after the first dose of the Pfizer-BioNTech vaccine and 28 days after the first dose of the Moderna vaccine), but since the goal of this study is to assess allergic reactions and not provide clinical vaccinations as indicated, subjects may be enrolled regardless of time elapsed since their initial vaccination. On day 1, they will be randomized at a 1:1 ratio to receive either placebo or the Pfizer-BioNTech vaccine. A pre-vaccination blood and urine sample will be obtained, and then the first dose (per randomization) of study vaccine will be given. Serial blood draws and the first void (urine) after the dose will be collected. Another post-vaccination void may be collected if an allergic reaction occurs after the first collection. The participant will be monitored by the principal investigator and/or an experienced allergist associate investigator for signs and symptoms of an allergic reaction and any other AE for a minimum of 3 hours, and medications and equipment will be immediately available to treat possible reactions. If a reaction does develop, the participant will be treated according to our study MOP, and additional urine samples may be collected to assess the immune response. If a skin rash develops, photographs may be taken to document variations in presentation. In case of a reaction after the first dose, the participant will be counseled and the second study vaccination will proceed as scheduled if the participant is willing. On day 2, the participant will receive either placebo or the Pfizer-BioNTech vaccine (whichever was not given on day 1) using the same procedure, but in the opposite arm. The participant will be monitored and treated (as needed) for an allergic reaction or AEs and samples will be collected as described for day 1. Participants will be discharged on day 3, unless they require additional treatment due to a reaction. Additionally, day 2 dosing may be delayed to a later day at the discretion of the investigator if the participant experiences an allergic reaction on day 1 that has not resolved by day 2 and does not rise to the level of a pausing or halting criterion (see sections 8.4.5 and 8.4.6). Day 2 dosing may be delayed for a maximum of 1 week. If the participant experiences other AEs (nonallergic in nature) on day 2 that are expected from the vaccine based on data from the Phase 3 trials (e.g. fatigue, headache, fever, myalgia), then the second study vaccination may still be given on day 2 as scheduled. A participant may be moved to a general ward after the completion of their vaccinations and close monitoring, when safe to do so.

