6.5 CONCOMITANT THERAPY

The following medications are prohibited during participation in the study:

- Systemic immunomodulators including systemic steroids.
- Biologic agents that will interfere with the study objectives at the discretion of the investigator.
- EUA monoclonal antibodies casirivimab and indevimab, or bamlanivimab, or any COVID-19-specific biologic including antibodies or immunomodulator for at least 5 half-lives.
- Zileuton.
- Any investigational or approved vaccines administered outside of the study prior to visit 3 and, for participants receiving a booster vaccination at visit 4, at least 2 months before visit 4 through visit 6.
- Any allergen immunotherapy administration within 24 hours prior to the first study vaccination through 24 hours after the second study vaccination, and from 24 hours prior to through 24 hours after visit 4 (for participants receiving the booster vaccination).

Since one of the goals of this study is to understand the mechanisms of allergic reactions to the COVID-19 vaccines, these medications have been excluded since they may interfere with analysis in mechanistic studies.

Participants may be asked to discontinue use of antihistamines and drugs with antihistamine properties prior to the study intervention as well as prior to skin testing at visit 3 or 4 and booster vaccination at Visit 4 (as applicable) since these medications can mask signs and symptoms of an allergic reaction, thereby reducing the accuracy of skin testing and affecting results of research tests following the booster vaccination. Participants will be asked to discontinue these medications for a time period equal to at least 5 half-lives of the medication prior to the study

intervention.^[31] These medications can be resumed once the participant is discharged at the end of Visit 1 and after Visit 3 or 4.

Unless medically contraindicated, participants may also be asked to discontinue use of beta blockers, ACE inhibitors, and NSAIDS that are thought to interfere with treatment of allergic reactions or that may act as eliciting factors that increase reactivity in susceptible individuals^[31] for a time period of 5 half-lives of the medication prior to the vaccine challenge at Visit 1 and the booster vaccination at Visit 4 (as applicable). They can resume these medications once they complete the study interventions at the respective visit.

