9.4.3 Analysis of the Secondary Endpoint(s)

Analyses to simple single proportion estimates will follow the same approach described for the primary endpoint.

Analysis of risk difference between active and placebo vaccines will be addressed in 2 separate ways. First, using only data from the first study vaccination, the risk difference will be estimated (proportion with systemic reaction in the active vaccine arm minus the analogue in the placebo arm) with an unconditional exact confidence interval. The second approach will exploit the crossover design (i.e., comparing each individual's active vaccine to placebo response), by estimating the risk difference using a McNemar's approach to an exact confidence interval.[\[34\]](#) While the McNemar's approach should be more precise than the group comparison approach at the first study vaccination, the potential for missing data on the second study vaccination, especially in the initial vaccine arm is not ideal. If there are such missing data, the second study vaccination will be imputed in the most extreme ways (i.e., smallest risk difference and largest risk difference) to see if the results are robust.

Hypothesis testing can be done for the active vaccine versus placebo risk difference. A Fishers exact test will be done when comparing the randomized arm at the first study vaccination. An exact McNemar's test will be done when comparing the within-subject differences. Approaches to missing data for McNemar's follow the estimation approaches.

A signed rank test will also be done to compare severity of reaction at the first vaccine (i.e., done prior to enrollment) to active study vaccine (where the difference in grade is the metric). Since that analysis assumes grade is linear, these data will also be analyzed using a purely ordinal approach to grade using a longitudinal GEE model with a cumulative logit link; this is effectively a generalization of McNemar's test, but for ordinal instead of binary data. Tabular data will also be presented.

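### Sections 9.4.2 and 9.4.3 protect the second-injection outcome only when it is missing, not when it may have been recorded under rescue antihistamine given for a Day 1 reaction

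*Combined protocol and SAP*

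**What the plan says.** Section 6.5 says participants may be asked to stop antihistamines because "these medications can mask signs and symptoms of an allergic reaction". The stop is "for a time period equal to at least 5 half-lives of the medication prior to the study" intervention, and the section adds: "These medications can be resumed once the participant is discharged at the end of Visit 1". Discharge comes after both injections.

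Section 4.1 covers a participant who reacts on Day 1: "the participant will be treated according to our study MOP", and "the second study vaccination will proceed as scheduled if the participant is willing". Dosing may be delayed, at the investigator's discretion and for at most a week, "if the participant experiences an allergic reaction on day 1 that has not resolved by day 2". Section 8.2.1 uses the 24-hour blood sample after the first injection as the baseline for the second, so the usual gap is about 24 hours. Under 6.3, reactions of CoFAR Grade 3 or lower are treated without unblinding. Section 4.2 expects some false-positive reactions, which is why there is a placebo.

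Section 9.4.2 estimates the primary endpoint as the proportion reacting to active vaccine, pooled over both orders, with a Clopper-Pearson interval. If a placebo-first participant does not get the active vaccine, there is a complete-data analysis and an "analysis where missing data is imputed to be a vaccine reaction". Section 9.4.3 has a parallel rule for the paired comparison: "If there are such missing data, the second study vaccination will be imputed in the most extreme ways". Section 9.1 also lists the proportion reacting to each injection, before and after crossover, by arm.

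**The concern.** Both safeguards are triggered by a missing second-injection outcome. Neither covers an outcome that was observed but may have been suppressed by treatment given the day before. A reaction that resolved because it was treated is not a listed ground for delay.

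For the primary endpoint, the exposed group is placebo-first participants who react to placebo, are given a masking drug, and receive the active vaccine before that drug has washed out. Masking can turn a vaccine reaction into a recorded non-reaction, but not the reverse. Any bias therefore makes re-vaccination look safer than it is, which is the wrong direction for a safety study. CoFAR Grade 2 can be met by two mild organ systems among skin, upper airway, eye and gut (Appendix A), so even partial masking could change the classification. The plan already counts an unobserved vaccine outcome as a reaction in its fallback analysis. It has no such check on an outcome observed under a drug of the kind that 6.5 says can mask reactions.

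**Working it through.** **The plan's own figures.** Clopper-Pearson limits reproduce Table 5: 2/10 gives 0.025–0.556, 32/40 gives 0.644–0.909, and 80/100 gives 0.708–0.873.

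**Washout.** A 24-hour gap covers 5 half-lives only if the half-life is at most 24/5 = 4.8 h. The documents give no half-lives. If 8 h or 12 h is assumed, the fraction left at 24 h is 0.5^(24/8) = 12.5% or 0.5^(24/12) = 25%. Five half-lives leave 0.5^5 = 3.1%.

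**Shift in the primary estimate.** Let m be the share of placebo-first placebo reactors whose vaccine reaction is masked. This is assumed; the documents do not give it. Order is randomized 1:1, so half the sample is placebo-first:

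shift = −m × P(reacts to both) / 2

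Table 7 assumes that everyone who reacts to placebo also reacts to vaccine (nesting, section 9.2). At .80 vaccine and .20 placebo, P(both) = 0.20. The shift is then −0.025, −0.05 and −0.10 for m = 0.25, 0.5 and 1. If the two reactions are independent, P(both) = 0.80 × 0.20 = 0.16 and the largest shift is −0.08.

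| .80 v .20, nested | m = 0 | m = 0.5 | m = 1 |
|---|---|---|---|
| N=40 estimate | 32/40 (0.644–0.909) | 30/40 (0.588–0.873) | 28/40 (0.535–0.834) |
| N=40 coverage of 0.80 | 0.973 | 0.897 | 0.707 |
| N=100 estimate | 80/100 (0.708–0.873) | 75/100 (0.653–0.831) | 70/100 (0.600–0.788) |
| N=100 coverage of 0.80 | 0.967 | 0.794 | 0.373 |

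For coverage, the vaccine-first half is Binomial(N/2, p) and the placebo-first half is Binomial(N/2, p − m × P(both)), where p is the true vaccine reaction rate. The two are convolved exactly.

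**Lower rates.** Assume 20% on vaccine and 5% on placebo. Nested, the largest shift is −0.05/2 = −0.025. At N=40, 8/40 (0.091–0.356) becomes 7/40 (0.073–0.328). Coverage at m = 1 is 0.974 for N=40 and 0.946 for N=100. If independent, P(both) = 0.20 × 0.05 = 0.01 and the largest shift is −0.005.

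**Paired difference, N=40, .80 v .20, nested, full masking in both orders.** Vaccine-first gives 16 vaccine-only and 4 neither. Placebo-first gives 12 vaccine-only, 4 placebo-only and 4 neither. The estimate is (28 − 4)/40 = 0.60, unchanged, but the interval widens from 0.369–0.751 (Table 7) to about 0.32–0.79. Full masking in only one order moves the estimate: placebo-first only gives (24 − 4)/40 = 0.50, and vaccine-first only gives 28/40 = 0.70.

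**What is unaffected.** The vaccine-first half of the primary estimate, the pre-crossover vaccine proportion in 9.1, and the first-vaccination risk difference in 9.4.3 do not use a second-injection outcome. At N=40 and .80, the pre-crossover proportion would be 16/20 (0.563–0.943 in Table 5's N=20 row).

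**The case against.** The rescue drug is not named. Treatment follows the MOP, section 2.3.1 gives only routes of administration, and the antihistamine mention in 2.3.3 concerns an outside case series. If the MOP already delays the second injection after an antihistamine, the gap closes. This stands: antihistamine rescue is an inference.

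A reader might infer that 4.1 contradicts 6.5. The text does not support that. Section 6.5 is conditional (participants may be asked), concerns participants' own medicines, and names skin testing and booster research tests as what masking would affect. Section 4.1 concerns treating a reaction. Applying 6.5 to rescue drugs is an extension of its reasoning. That extension is reasonable, because the requested stop also precedes the study intervention and 5.5 asks participants to stop drugs that might interfere with the vaccine challenge.

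Section 9.1 already plans an unaffected vaccine proportion. This also stands, but that proportion does not show who was medicated, and the primary estimate still pools both orders.

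The single m is crude. Grade 3 reactions may be harder to mask, and Grade 1 with elevated tryptase still counts as an event, so some partly masked reactions would be captured. These points argue for a small m, not for m = 0. Placebo reactors are also where anxiety mimics are expected, so counting their non-reactions as reactions may overshoot. The result should therefore be read as a bound.

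**Conclusion.** The point holds as a modest gap in the sensitivity analyses. The second-injection safeguards depend on missingness, and nothing in the plan flags or re-analyses an outcome recorded after rescue treatment. If rescue antihistamine is used and active vaccine follows within the washout period, the pooled primary rate can only be biased downward. The size is m × P(reacts to both)/2: at most 0.10 in the plan's .80/.20 illustration, at most 0.025 with little loss of coverage at 20% v 5%, and zero if no placebo reactor is medicated.

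A reader might infer from the 0.373 coverage that the primary interval is unreliable. The documents do not support that. The figure needs N=100, illustrative rates given only to show precision, full nesting, and an assumed m of 1. Nor do the documents show that any participant was dosed under a masking drug.

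**What to change.** **Section 9.4.2.** Keep the observed outcome in the primary estimate and add:

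- Report the number of placebo-first participants who received active vaccine within 5 half-lives of a Day 1 rescue antihistamine, or after any Day 1 rescue systemic steroid. No half-life rule is attached to steroids, because 6.5 gives none.
- Add a sensitivity analysis that counts these participants' recorded non-reactions as reactions, as in approach (ii).
- Present the first-injection vaccine proportion from 9.1, with its Clopper-Pearson interval, beside the primary estimate.

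**Section 9.4.3.** Extend the existing extreme imputation (smallest and largest risk difference) to second-injection non-reactions recorded under Day 1 rescue medication, in either order.

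**Cost.** A few sentences of analysis text. No endpoint is re-scored. The data should exist, since 8.2.1 reviews concomitant medication after enrollment, though the time of each rescue dose is needed. The bound overstates the rate by 1/40 = 0.025 per participant at N=40 if a medicated participant would truly not have reacted. If the count is zero, reporting it settles the matter.

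Allowing the Day 2 delay to run until 5 half-lives after the rescue drug is optional and probably moot. Section 4.1 notes that only 2 participants had yet to complete the 5-month visit by mid-September 2022, so Visit 1 dosing appears complete. Because 6.3 unblinds after the last Visit 1, an analysis added after that should be labelled post hoc.

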9.4.3 Analysis of the Secondary Endpoint(s)

Analyses to simple single proportion estimates will follow the same approach described for the primary endpoint.

Analysis of risk difference between active and placebo vaccines will be addressed in 2 separate ways. First, using only data from the first study vaccination, the risk difference will be estimated (proportion with systemic reaction in the active vaccine arm minus the analogue in the placebo arm) with an unconditional exact confidence interval. The second approach will exploit the crossover design (i.e., comparing each individual's active vaccine to placebo response), by estimating the risk difference using a McNemar's approach to an exact confidence interval.[\[34\]](#) While the McNemar's approach should be more precise than the group comparison approach at the first study vaccination, the potential for missing data on the second study vaccination, especially in the initial vaccine arm is not ideal. If there are such missing data, the second study vaccination will be imputed in the most extreme ways (i.e., smallest risk difference and largest risk difference) to see if the results are robust.

Hypothesis testing can be done for the active vaccine versus placebo risk difference. A Fishers exact test will be done when comparing the randomized arm at the first study vaccination. An exact McNemar's test will be done when comparing the within-subject differences. Approaches to missing data for McNemar's follow the estimation approaches.

A signed rank test will also be done to compare severity of reaction at the first vaccine (i.e., done prior to enrollment) to active study vaccine (where the difference in grade is the metric). Since that analysis assumes grade is linear, these data will also be analyzed using a purely ordinal approach to grade using a longitudinal GEE model with a cumulative logit link; this is effectively a generalization of McNemar's test, but for ordinal instead of binary data. Tabular data will also be presented.

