2.3.3 Assessment of Potential Risks and Benefits

In a case series study of 159 patients, including 19 who met anaphylaxis criteria after the first dose of an mRNA COVID-19 vaccine, all 159 patients tolerated the second dose.^[30] Thirty-two (20%) reported immediate and potentially allergic symptoms that were associated with the second dose that were self-limited, mild, and/or resolved with antihistamines alone. However, individuals who experience a systemic allergic reaction following the first dose of the Pfizer-BioNTech or Moderna vaccines are advised not to receive a second dose according to current FDA and CDC guidelines. Although the efficacy of a single dose of these vaccines has not been systematically studied, 2 doses of the vaccine may be necessary for full efficacy. Whether a second dose with a discordant vaccine from that given as the first dose is as effective as receipt of the same vaccine for both doses is unknown. Because of the potential role for PEG as the culprit trigger for these allergic reactions, these individuals may also be advised to avoid any new COVID-19 vaccines under development that contain PEG or the cross-reactive polysorbate 80, limiting their access to vaccines that protect against COVID-19. Clarification of the mechanisms underlying allergic reactions in this population will facilitate risk factor analysis to improve patient selection for these vaccines and potentially improve the design of future vaccines using this platform.

To maximize safety, all participants will be admitted to the Intensive Care Unit (ICU) at the Clinical Center for visit 1, where experienced staff and all equipment and medications necessary to treat severe allergic reactions are readily available. Participants receiving a booster vaccination at visit 4 will be monitored closely for at least 2 hours after administration, with staff, equipment, and medications readily available in case of an allergic reaction. Patients will also be screened by phone prior to enrollment to ensure that other comorbid conditions (e.g. asthma) that may increase the risk of a severe reaction are stable. If sufficient information cannot be obtained over the phone, or additional testing (e.g., pulmonary function tests) is felt to be necessary to make this assessment, potential subjects may be asked to come to the NIH for additional testing before enrollment.

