6.3 MEASURES TO MINIMIZE BIAS: RANDOMIZATION AND BLINDING

Participants will be randomized to receive either Pfizer-BioNTech vaccine or placebo on Day 1 in a 1:1 ratio at enrollment via block randomization. On Day 2, subjects will receive whichever of vaccine or placebo that was not given on Day 1. A randomization scheme will be generated by the NIAID Biostatistics Research Branch who will provide a randomized list of arm assignments to the NIH Clinical Center Pharmacy. The randomization code list will be maintained by the Investigational Drug Control Unit (IDCU) in the electronic Investigational Drug Management System (IDMS).

The participants, the clinical staff, and the study team will be blinded to the order of study vaccine assignments. The unblinded pharmacy staff is responsible for maintaining security of the assignments.

Intentional unblinding: Unblinding will occur after the last participant has completed Visit 1. There will be no emergency unblinding for CoFAR Grade 3 or lower reactions because allergic and anaphylactic reactions to the vaccine are expected and will be treated per standard clinical care, and it is not necessary to unblind to do so. However, if a CoFAR Grade 4 or higher systemic allergic reaction or other life-threatening AE occurs, then both the investigator and the participant will be unblinded. If a CoFAR Grade 4 or higher reaction occurs on day 1, then the participant will not receive the study intervention the next day (either placebo or vaccine).

To break a treatment blind, the principal investigator will request a participant's treatment assignment from the IDCU. If an emergency request for treatment assignment is made by an individual other than the principal investigator and the principal investigator is not immediately available, the request will be made to one of the physician associate investigators, who will then contact the IDCU or appropriate NIH pharmacy after-hours contact to obtain the treatment assignment. If a participant's study agent assignment is unblinded, the information will be provided to only the individuals needing it for treatment decisions; all attempts will be made to maintain the blind of the study team.

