9.2 SAMPLE SIZE DETERMINATION

The goal is to enroll up to 100 subjects; however, realistically, it may only be possible to enroll a smaller cohort. The ability to recruit for this study will depend on the rarity of such allergic reactions in the population and the acceptability of repeat vaccination and a 4-day hospital stay among individuals who have had these reactions. Current data indicates an extremely low systemic reaction rate, although it is likely that the overall rate may be higher since individuals recruited for this study have a history of a systemic allergic reaction following administration of the first dose of the vaccine. In sum, the study will provide more precise estimates with greater enrollment; however, even if fewer than 100 subjects enroll, the resulting data will provide valuable new information.

Since the primary goal of the study is estimation, we present the following example exact confidence intervals as a function of varying sample size and varying outcomes to illustrate achievable precision of estimates. We present such confidence intervals for the primary endpoint,

and also estimation of the risk difference of active vaccine versus placebo vaccine. The difference between active and placebo can be estimated in 2 different ways: one compares the results in the randomized arms at the first shot; and the other compares results within a subject across the 2 study vaccinations, exploiting the crossover design. Tables below present a subset of example scenarios in the study.

Table 5: Exact 95% Clopper Pearson Confidence Intervals for Primary Outcome, by Sample Size and Proportion with Systemic Allergic Reaction to Second Dose

Total N	Observed Reaction Rate					
	.00	.20	.40	.60	.80	1.00
5	0-0.522	0.005-0.716	0.053-0.853	0.147-0.947	0.284-0.995	0.478-1
10	0-0.308	0.025-0.556	0.122-0.738	0.262-0.878	0.444-0.975	0.692-1
15	0-0.218	0.043-0.481	0.163-0.677	0.323-0.837	0.519-0.957	0.782-1
20	0-0.168	0.057-0.437	0.191-0.639	0.361-0.809	0.563-0.943	0.832-1
40	0-0.088	0.091-0.356	0.249-0.567	0.433-0.751	0.644-0.909	0.912-1
60	0-0.06	0.108-0.323	0.276-0.535	0.465-0.724	0.677-0.892	0.94-1
80	0-0.045	0.119-0.304	0.292-0.516	0.484-0.708	0.696-0.881	0.955-1
100	0-0.036	0.127-0.292	0.303-0.503	0.497-0.697	0.708-0.873	0.964-1

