As the sample size increases, precision in the estimate of the true proportion of subjects with a reaction to the second vaccine dose also increases. As an example, if the total N is 10, and there is .20 reaction rate (i.e., 2 react) to active vaccine, then the 95% CI for reaction rate is (.025, .556).

Table 6: Exact 95% Confidence Intervals for the Difference in Reaction Rate Between Vaccine and Placebo Arms on Day 1

Total N	Observed Reaction Rate per Arm on Day 1		
	1.00 Vaccine, .00 Placebo	.80 Vaccine, .20 Placebo	.60 Vaccine, .20 Placebo
6	0.082-1	-0.282-0.992	-0.554-0.889
10	0.383-1	-0.112-0.933	-0.268-0.858
20	0.663-1	0.127-0.862	-0.058-0.756
40	0.824-1	0.287-0.798	0.084-0.666
60	0.881-1	0.313-0.767	0.134-0.622
80	0.702-1	0.338-0.748	0.144-0.594
100	0.597-1	0.355-0.734	0.16-0.575

Note: If only 6 subjects are enrolled, a reaction rate of 80% in the vaccine arm corresponds to 3/3 reactions; a reaction rate of 60% in the vaccine arm corresponds to 2/3 reactions; and a reaction rate of 20% in the placebo arm corresponds 1/3 reactions.

Thus, if the total N is 20 with 10 on active vaccine on Day 1 and 10 on placebo, and 8 of those receiving active vaccine have a reaction and 2 of those receiving placebo have a reaction, the 95% CI for the excess reaction in active vaccine minus placebo is (.127, .862). Since this particular confidence interval does not include zero, this is also a demonstration that vaccines lead to excess reactions.

Table 7: Exact 95% Confidence Intervals for the Risk Difference Comparing each Individual's Vaccine Phase to Placebo Phase Response Using McNemar's Approach

Total N	Observed Reaction Rate per Treatment Phase		
	1.00 Vaccine, .00 Placebo	.80 Vaccine, .20 Placebo	.60 Vaccine, .20 Placebo
5	-0.044-1	-0.275-0.947	-0.369-0.853
10	0.338-1	0.04-0.878	-0.088-0.738
15	0.517-1	0.162-0.837	0.026-0.677
20	0.621-1	0.235-0.809	0.084-0.639
40	0.797-1	0.369-0.751	0.192-0.567
60	0.861-1	0.423-0.724	0.238-0.535
80	0.895-1	0.453-0.708	0.264-0.516
100	0.915-1	0.473-0.697	0.281-0.503

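### Section 9.4.3 names no ordering for the Day 1 exact interval; the ordering that reproduces Table 6 is valid but clearly wide at low reaction rates

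*Combined protocol and SAP*

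**What the plan says.** Section 9.4.3 analyses the vaccine-placebo risk difference in two ways. The first uses only the first study vaccination: the vaccine-arm proportion "minus the analogue in the placebo arm) with an unconditional exact confidence interval". No ordering statistic is given. For the same comparison the section adds a test: "A Fishers exact test will be done when comparing the randomized arm at the first study vaccination". The second way is a paired interval with a cited method.

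Section 9.2 illustrates the Day 1 interval in Table 6 for N from 6 to 100, at vaccine/placebo rates of 1.00/.00, .80/.20 and .60/.20. Its worked example, 8 of 10 v 2 of 10, says "the 95% CI for the excess reaction in active vaccine minus placebo is (.127, .862".

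On likely rates, Section 9.2 says "Current data indicates an extremely low systemic reaction rate" and adds that the rate may be higher in this cohort; it gives no figure. Section 2.3.3 cites a case series of 159 patients given a second dose, of whom "Thirty-two (20%) reported immediate and potentially allergic symptoms". On enrolment: "The goal is to enroll up to 100 subjects; however, realistically, it may only be possible to enroll a smaller cohort".

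**The concern.** Two unconditional exact intervals can both guarantee 95% coverage and still differ a good deal in width, because each ranks the possible tables by a different statistic. Section 9 says that no formal SAP will be written, so no later document is planned to settle the choice. The primary endpoint has a named method (Clopper-Pearson) and the paired analysis has a cited one. The Day 1 comparison, the only parallel-group randomised estimate, has neither.

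Table 6 points to a Fisher-type ordering. Such an ordering is fixed: it does not change with the risk difference being tested, so its limits can be loose away from zero. At the high rates in Table 6 this is hard to see. If reactions turn out to be uncommon, it shows up mainly in the upper limit, the figure a reader would use to judge how large an excess risk remains possible.

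**Working it through.** **Inputs**
- Allocation on Day 1 is "in a 1:1 ratio at enrollment via block randomization" (Section 6.3), so n = N/2 per arm.
- Level: 95%, taken as 0.025 per tail; Section 9.4.1 says "two-sided p-values with alpha=.05 will be used".
- Printed limits: Table 6.
- Low-rate cells: 20% v 10% and 20% v 0% are assumptions, since the protocol gives no expected rate. The 20% echoes 32/159 = 0.201 in Section 2.3.3, which is not the CoFAR endpoint.

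**Method.** Let δ be the vaccine rate minus the placebo rate. The lower limit is the smallest δ0 not rejected by a one-sided 0.025 test, with the tail probability maximised over the placebo rate p. The upper limit is the mirror image. Only the ordering statistic is left to choose:
- Fisher mid-p: P(X_v > x_v | total) + ½·P(X_v = x_v | total), hypergeometric, the same for every δ0.
- Score (Farrington-Manning): z(δ0) = (p̂_v − p̂_p − δ0) / √[p̃_v(1−p̃_v)/n + p̃_p(1−p̃_p)/n], where p̃_v and p̃_p are the maximum-likelihood rates under p̃_v − p̃_p = δ0.

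**Step 1: reproduce Table 6.** For 8/10 v 2/10, Fisher mid-p gives (.127, .862), as printed; the score ordering gives (.127, .885). In the .80/.20 and .60/.20 columns (14 cells), Fisher mid-p matches 13 cells to three decimals. The remaining limit (N=10, .60/.20, lower −0.268) is reached once the tie between 3/5 v 1/5 and 4/5 v 2/5 is broken. A pooled Wald ordering matches 7 cells; score and simple-difference orderings match 1 each. The printed lower limits .313 (N=60, .80/.20), .338 and .144 (N=80), and .355 and .16 (N=100) arise only under Fisher ordering; score gives .342, .385, .182, .413 and .195.

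**Step 2: low rates, single cells**

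| N | Observed | Fisher mid-p | Width | Score | Width | Fisher wider by |
|---|---|---|---|---|---|---|
| 20 | 2/10 v 1/10 | (−.280, .539) | .819 | (−.280, .464) | .744 | .819/.744 − 1 = 10% |
| 40 | 4/20 v 2/20 | (−.182, .415) | .597 | (−.144, .350) | .494 | .597/.494 − 1 = 21% |
| 100 | 10/50 v 5/50 | (−.066, .318) | .384 | (−.046, .249) | .295 | .384/.295 − 1 = 30% |
| 40 | 4/20 v 0/20 | (.000, .587) | .587 | (.014, .437) | .423 | .587/.423 − 1 = 39% |
| 100 | 10/50 v 0/50 | (.098, .521) | .423 | (.098, .337) | .239 | .423/.239 − 1 = 77% |

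The first three rows were unchanged on a 3,001-point grid for p. Averaged over possible data at N=20, the excess is .827/.724 − 1 = 14% for true rates of 20% v 10%, and .805/.678 − 1 = 19% for 20% v 0%.

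**Step 3: high rates**
- .80/.20, N=20: printed width .862 − .127 = .735; score .885 − .127 = .758. Score is .758/.735 − 1 = 3% wider.
- .80/.20, N=40: printed .798 − .287 = .511; score .819 − .274 = .545. Score is .545/.511 − 1 = 7% wider (put the other way, the printed interval is 6% narrower).
- .80/.20, N=100: printed .734 − .355 = .379; score .747 − .413 = .334. Here the printed interval is 13% wider.

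**Step 4: the 1.00/.00 column.** The table n/n v 0/n is the most extreme one. Its probability is [(p+δ)(1−p)]^n, largest at p = (1−δ)/2, where it equals [(1+δ)/2]^N. Setting this to 0.025 gives the lower limit 2·0.025^(1/N) − 1. This agrees with the printed limits for N=6 to 60 to within 0.001; at N=60 it is 2(0.9404) − 1 = 0.881. At N=80 it is 2(0.9549) − 1 = 0.910 (printed 0.702), and at N=100 it is 2(0.9638) − 1 = 0.928 (printed 0.597). The printed limits fall as N rises, which they should not. Rounded Fisher p-values that tie near zero give similarly low limits, a possible cause.

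**The case against.** The case for leaving the plan alone has real substance.

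- **The interval is valid.** A Fisher-ordered unconditional interval keeps at least 95% coverage, and it is a natural companion to the planned Fisher's exact test. The protocol does not give that reason, but it is a fair one. This stands: the issue is efficiency, not error.
- **The text does not commit to it.** A reader might infer from Table 6 that the protocol has fixed an inefficient interval. Section 9.4.3 names no ordering, and Section 9.2 offers the tables as examples of achievable precision. The supportable point is an open choice, with Table 6 showing where it may lead.
- **No low rate is stated.** A reader might also infer that the protocol expects rates of 10-20%. It does not say so. The 20% in Section 2.3.3 counts symptoms described as mild, self-limited and/or resolved with antihistamines alone, in a series where only 19 of 159 met anaphylaxis criteria after the first dose. Section 2.3.1 says participants are likely at higher risk than the general population.
- **No single percentage describes the loss.** It depends on N and on the placebo rate. When both arms have the same count it also depends on how Fisher ties are broken: at 10% v 10% and 20% v 20%, with ties broken, it ranges from −3% to +41%.
- **Score ordering is not uniformly better.** At .80/.20 it raises the upper limit: .862 to .885 at N=20, .798 to .819 at N=40.
- **Reach and timing.** This is one of two analyses of one secondary endpoint; the primary endpoint and the enrolment target do not depend on it. Section 4.1 notes that by mid-September 2022 only two participants had yet to complete the 5-month visit, and that unblinding follows the last Visit 1. Dosing at Visit 1 may therefore be over. The documents do not say whether unblinding has occurred.

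**Conclusion.** The concern holds as a minor point. The ordering in 9.4.3 is unspecified, and the one that reproduces Table 6 costs precision at low rates: 10% to 30% extra width in the 20% v 10% cells from N=20 to N=100, and 39% to 77% in the 20% v 0% cells at N=40 and N=100. In the largest case, 10/50 v 0/50, the upper limit is .521 rather than .337.

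This rests on equal arms, 0.025 per tail, and low rates that are assumed rather than stated. It also needs the score statistic recomputed at each δ0; a pooled Wald ordering, which fixes the statistic at δ=0, gives nearly the same widths as Fisher. Were the reaction rates close to those in Table 6, the choice would matter much less and at N=20-40 could go slightly the other way.

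Separately, and whatever ordering is chosen, the 1.00/.00 lower limits at N=80 and N=100 cannot be right.

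**What to change.** Before unblinded analysis, state in 9.4.3 that the Day 1 interval inverts two one-sided 0.025 unconditional exact tests, ordered by the Farrington-Manning score statistic evaluated at each tested difference and maximised over the nuisance rate. Recompute Table 6 on that basis, add .20/.00 and .20/.10 columns, and correct the 1.00/.00 lower limits at N=80 and N=100 to about 0.910 and 0.928. If unblinding has already happened, label the choice as made afterwards and show the Fisher-ordered interval beside it.

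The cost is one sentence, a software option and one recomputed table. There are two downsides:
- At .80/.20 the score interval is about 3% (N=20) to 7% (N=40) wider, with an upper limit about .02 higher.
- It need not agree with the planned Fisher's exact test. For 4/20 v 0/20 the score interval (.014, .437) excludes zero, while Fisher's two-sided p is 2 × C(20,4)/C(40,4) = 2 × 4,845/91,390 = 0.106. Section 9.4.3 should say how such a case will be reported; since Section 9.1 puts estimation first, leading with the interval would be consistent with the plan.
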